12.9. Efficacy

12.9.1. Double-Blind Period

The primary efficacy analysis will be based on the FAS population defined for the double-blind period of the study (see [Section 12.3](#)). For each patient, the change from Baseline in PKAN-ADL scores at Weeks 3, 6, 12, 18, and 24 of the double-blind period will be used for analysis. The treatment effect will be evaluated on the basis of mixed model for repeated measures (MMRM) analysis to assess data from all visits simultaneously. The model will include fixed effects for treatment, age stratum (6 to <18 or 18 to 65 years), visit and treatment by-visit interaction, a random effect for patient within treatment group, and Baseline

PKAN-ADL score as a covariate. The PKAN-ADL measurement obtained prior to the first dose of investigational product will serve as each patient's Baseline value. Least-squares adjusted means and the adjusted mean difference between treatment groups will be reported at each study visit, along with 2-sided 95% confidence intervals (CIs) and the p-value for the treatment comparison.

The mixed-effect linear model will be implemented using PROC MIXED in SAS with the restricted maximum likelihood (REML) estimation method and Kenward-Roger degrees of freedom algorithm for the F-test. Significance tests will be based on least squares means using Type III sum of squares.

To support the primary efficacy analysis, analysis of covariance (ANCOVA) models will be applied to change from Baseline in PKAN-ADL scores assessed after 3, 6, 12, 18, and 24 weeks of treatment. For each week analyzed, the model will include treatment and age stratum (6 to <18 or 18 to 65 years) as fixed effects and Baseline PKAN-ADL score as a covariate. Estimates of the adjusted mean treatment differences and the 2-sided 95% CIs at each time point will be obtained from the model.

Secondary and exploratory efficacy endpoints that are continuous measures recorded at each study visit will be evaluated using the MMRM approach described above for the primary efficacy endpoint. Summary statistics for efficacy measures will include graphical plots of mean and mean change from Baseline values at each study visit, by treatment group.

Treatment effects on categorical outcomes will be examined using frequency tables and tested using Cochran-Mantel-Haenszel chi-square methods with stratification by age group (6 to <18 or 18 to 65 years).

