Patients with PKAN-ADL administration errors will be included in the Double-Blind FAS, but excluded from the PPS, as per [Section 4.5](#). Imputation rules for the data affected by the translation issue can be found in [Section 4.1](#).

The linear mixed-effect model will be implemented using PROC MIXED in SAS with the restricted maximum likelihood (REML) estimation method. An unstructured variance-covariance matrix will be used to model the within-patient errors. [Note: In the unlikely event that the computational algorithm fails to converge, the following structures will be executed in the order specified (essentially in decreasing order of complexity) until convergence is achieved: Toeplitz with heterogeneity, autoregressive with heterogeneity by Week, compound symmetry with heterogeneous variances by Week, autoregressive, Toeplitz, and compound symmetry without heterogeneous variances by Week.]

Significance tests will be based on least squares means (LSMs) using Type III sum of squares. The Kenward and Roger method will be used for calculating the denominator degrees of freedom for tests of fixed effects.

The PROC MIXED SAS coding is as follows:

```
proc mixed data=DATA;
    class TRT WEEK PATIENT;
    model C_score = BASE_score AGE TRT WEEK TRT*WEEK / solution
    ddfm=kr;
    repeated WEEK / subject=PATIENT type=un;

run;

where:
    TRT = treatment group (0 = placebo, 1 = fosmetpantotenate)
    WEEK = week 3, 6, 12, 18, 24
    AGE = age group (0=Pediatric, 1= Adult)
    C_score = change in score from baseline
    BASE_score = baseline score
```

The LSMS for each treatment, the difference between the LSMSs, and the standard error (SE) and 95% confidence interval (CI) associated with the difference will be reported at each study visit. The primary treatment comparison will be based on the test of contrast between treatment effects using the LSM estimate at Week 24, adjusted for baseline score and age group from the Type III analysis.

To estimate the mean change from baseline for PKAN-ADL total scores in each treatment group (placebo or fosmetpantotenate) at Week i ($i = 3, 6, 12, 18$, and 24), the following estimate statement (as an example) will be utilized:

```
estimate 'Placebo Group at Week 24'
    intercept 1
    AGE        <proportion in age group=0  proportion in age group=1>
    BASE_score <mean of BASE_score>
    TRT        1 0
    WEEK       0 0 0 0 1
    TRT*WEEK   0 0 0 0 1
                0 0 0 0 0 / cl;

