estimate 'FOSMETPANTOTENATE Group at Week 24'
    intercept 1
    Age        <proportion in age group=0  proportion in age group=1>
    BASE_score <mean of BASE_score>
    TRT        0 1
    WEEK       0 0 0 0 1
    TRT*WEEK   0 0 0 0 0
                0 0 0 0 1 / cl;
```

To estimate the treatment effect (i.e., the difference between fosmetpantotenate and placebo) at Week i ($i = 3, 6, 8, 12$, and 24), the following estimate statement (as an

example) will be utilized:

```
estimate 'Treatment Effect at Week 24'  
    TRT      -1 1  
    TRT*WEEK  0 0 0 0 -1  
              0 0 0 0 1 / cl;
```

The point estimates and corresponding 95% CIs for the treatment effect at each week will be presented for the FAS (double-blind period).

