4.10.2 Secondary Efficacy Endpoint

Part III of the UPDRS consists of 27 items, which correspond to 14 domains related to motor abilities such as tremor, stability, and bradykinesia. Each item has responses ranging from 0-4, with a higher value indicating greater disability. To compute the UPDRS Part III total score, responses are summed across the 27 items, and accordingly, will range from 0-108. For domain totals, responses will be summed across all of the items in a given domain (when domain corresponds to multiple items).

For analysis purposes, data from the pediatric and adult age groups will be pooled. All descriptive summary tables will be repeated using age group as a subgroup.

Descriptive statistics will be presented for the UPDRS Part III total score, with absolute and percent change from baseline, by treatment group for each visit of the double-blind period. For post-baseline assessments, categories for change from baseline UPDRS Part III total score (e.g., >0 , $=0$, <0 , ≤ -1 , ≤ -2 , ≤ -3 , ≤ -4), categories for percent improvement (i.e., decrease) in UPDRS Part III total score from baseline (i.e., $<0\%$, $=0\%$, $>0\%$, $\geq 10\%$, $\geq 20\%$, $\geq 30\%$, $\geq 40\%$, $\geq 50\%$), and categories for UPDRS Part III total score status (improvement, no change, or worsening) will be presented. These categories may be adjusted in a way that ensures that the categories contain at least 10% of patients. This will be run using the Double-Blind FAS and repeated using the PPS, as a sensitivity analysis.

Frequency tables will display change from baseline for each of the 14 domains, by treatment group for each visit of the double-blind period, using categories for change from baseline domain score (i.e., >0 , $=0$, <0 , ≤ -1 , ≤ -2 , ≤ -3), and categories for domain score status (improvement, no change, or worsening). These summaries will be run using the Double-Blind FAS and repeated using the PPS, as a sensitivity analysis.

The MMRM model described above for the primary efficacy endpoint will also be performed for the secondary efficacy endpoint: change from baseline UPDRS Part III total score. The LSMs for each treatment, the difference between the LSMs, and the standard error (SE) and 95% confidence interval (CI) associated with the difference will be reported at each study visit. The analysis will be based on the Double-Blind FAS, and will be repeated using the PPS, as a sensitivity analysis.

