4.10.3 Exploratory Efficacy Endpoints

Exploratory efficacy endpoints that are continuous rating scales recorded at multiple post-baseline visits (i.e., BAD Scale, Neuro-QOL, Euro-QOL, 25-foot walk test) will be evaluated using the MMRM approach described above for the primary efficacy endpoint. For endpoints obtained only at the baseline and final (Week 24) visits of the double-blind period (i.e., FIM/WeeFIM, DDK), the ANCOVA model will be used. The model will be run using the observed case (OC) procedure only. Summary statistics for efficacy measures will include graphical plots of mean and mean change from baseline values at each study visit during the double-blind period, by treatment group.

For analysis purposes, data from the pediatric and adult age groups will be pooled. All descriptive summary tables will be repeated using age group as a subgroup.

Treatment effects on categorical outcomes will be examined using frequency tables and tested using the Cochran-Mantel-Haenszel (CMH) chi-square methods with stratification by age group (pediatric, adult) ([Mantel and Haenszel, 1959](#)).

For the Interim Analysis, the Double-Blind FAS only will be used for analyses involving exploratory efficacy endpoints.

Statistical methods and estimation procedures are described below for each of the exploratory endpoints.

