6.1.5 Body of the Data Display

1. Listings will be sorted for presentation in order of study phase, treatment group, as above, patient ID, collection day, and collection time.
2. For ordered categorical parameters, frequency tables will present all categories of the parameter between the minimum and maximum level, even if n=0 for all treatment groups in a given category. For example, the frequency distribution for symptom severity would appear as:

Severity Rating	n
severe	0
moderate	8
mild	3

Where percentages are presented in these tables, any counts of 0 will be presented as 0 and not as 0 (0%).

3. If the categories for a table are not ordered (e.g., Medical History, Reasons for Discontinuation from the Study, etc.), then only those categories for which there is at least 1 patient represented in 1 or more groups will be included.
4. An Unknown or Missing category will be added to the summary table of any categorical parameter for which information is not available for 1 or more patients.
5. Unless otherwise specified, the estimated mean and median for a set of values will be displayed to 1 more significant digit greater than the original values; standard deviation (SD) will be presented to 2 more significant digits than the original values. The minimum and maximum will be reported at the same number of significant digits as the original values. LSmeans will be reported to 1 decimal place, and corresponding CI's to 2 decimal places. For example, for systolic blood pressure:

n	XX
Mean	XXX.X
SD	X.XX
Median	XXX.X
Minimum	XXX
Maximum	XXX

6. Data in columns of a table will be formatted as follows:
 - alphanumeric values left-justified;
 - whole numbers (e.g., counts) right-justified; and
 - numbers containing fractional portions decimal-aligned.
7. Percentage values will be formatted with 1 digit to the right of the decimal point in parentheses, 1 space after the count (e.g., 7 (12.8%), 13 (5.4%)). Less-than signs (e.g., “<0.1%”) will appear when values are >0.0% and <0.1% (but not equal to 0.0%). Unless otherwise noted, the denominator for calculating percentages will be the number of patients in a given treatment group and analysis set.

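### The primary PROC MIXED code leaves AGE out of CLASS but gives it two ESTIMATE coefficients, so the per-arm adjusted means come out at the wrong age mix or not at all; the treatment difference is unaffected

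*SAP*

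**What the plan says.** The text of SAP 4.10.1 describes age group as a two-level fixed effect. The code beneath it has the CLASS line "class TRT WEEK PATIENT" and puts AGE in the MODEL statement. The coding key reads "AGE = age group (0=Pediatric, 1= Adult". The ESTIMATE statements for placebo and for fosmetpantotenate both give AGE a pair of coefficients, beginning with "<proportion in age group=0" and followed by the proportion in group 1. The ESTIMATE statement for the treatment effect has no AGE term. The PROC MIXED code contains no LSMEANS statement.

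Per-arm results are required output. Protocol 12.9.1 says "Least-squares adjusted means and the adjusted mean difference between treatment groups will be reported at each study visit", with 95% confidence intervals, and the arm ESTIMATE statements carry the option that prints confidence limits. SAP 6.1.5 adds that "LSmeans will be reported to 1 decimal place".

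The model is reused. For UPDRS Part III, SAP 4.10.2 says "The MMRM model described above for the primary efficacy endpoint will also be performed for the secondary efficacy endpoint". For exploratory scales measured at several visits, SAP 4.10.3 says they "will be evaluated using the MMRM approach described above for the primary efficacy endpoint".

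The PROC GLM code for the ANCOVA sensitivity analysis in SAP 4.10.1.1 does list AGE in its CLASS statement.

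**The concern.** A numeric 0/1 variable has one regression parameter, here the adult-minus-pediatric difference. The only coefficient that puts an arm mean at the trial's age mix is the adult proportion. Two coefficients make sense only if AGE is a classification factor with two levels. Because the pediatric proportion comes first, reading the first number and dropping the second multiplies the adult effect by the pediatric share. The other possibility is that the statement fails.

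At stake is the description of each arm. The arm means show whether treated patients improved or only declined less than placebo. Protocol 4.2 raises both possibilities: improvement in signs and symptoms, and stabilization of progression. A common shift in both arms leaves the difference intact but can change how each arm's course reads, and it would not show up in the primary comparison.

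**Working it through.** **Inputs.** SAP 4.2 gives 37 patients per arm, SD 4.5, a 3-point difference and two-sided alpha 0.05. SAP 4.10.1 gives five post-baseline visits. The pediatric share p, the age effect β (adult minus pediatric) and the between-visit correlation ρ are not in the documents, so ranges are assumed.

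**The plan's own figure.** The standard error of the difference is 4.5 × √(2/37) = 1.046. Power for 3 points with 72 degrees of freedom is 80.8%, which agrees with the stated approximate 80%. That figure is not in dispute.

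**Shift in each arm mean, if the surplus coefficient is ignored.**
- Coefficient used: p. Coefficient needed: 1 − p.
- Shift = β × [p − (1 − p)] = β × (2p − 1), the same in both arms and at every visit.
- The shift reaches 0.1 point, visible at one-decimal reporting, when |β| = 0.1/|2p − 1|.

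| Assumed p | Size of shift per 1 point of β | β giving a 0.1-point shift |
|---|---|---|
| 40% | 0.2 | 0.50 |
| 30% | 0.4 | 0.25 |
| 20% | 0.6 | 0.17 |

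At p = 50%, or with β = 0, there is no shift.

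**Standard error of each arm mean.** Assume complete data, equal age shares in the two arms and compound symmetry. The correct Week 24 standard error is 4.5/√37 = 0.740. Evaluating at the wrong age share adds (2p − 1)² times the variance of the age coefficient. The ratio of literal to correct standard error is therefore

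√{1 + 0.5 × [(1 + 4ρ)/5] × (1 − 2p)²/[p(1 − p)]}.

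SD, sample size and β all cancel from this ratio. Example with p = 0.3 and ρ = 0.5: √(1 + 0.5 × 0.6 × 0.16/0.21) = √1.2286 = 1.108.

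| Assumed p | ρ = 0.5 | ρ = 0.7 | ρ = 0.9 | AR(1), ρ 0.5 to 0.9 |
|---|---|---|---|---|
| 40% | 1.025 | 1.031 | 1.038 | 1.018–1.034 |
| 30% | 1.108 | 1.136 | 1.162 | 1.079–1.147 |
| 20% | 1.294 | 1.362 | 1.427 | 1.217–1.389 |

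Across both correlation patterns the arm intervals are 2–4%, 8–16% and 22–43% too wide.

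**Treatment difference.** A 0/1 column and a two-level factor span the same model, and the difference contrast has no AGE term. Its standard error is 1.046 in every case above.

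**Numerical check.** One simulated dataset of 82 complete patients was fitted with an unstructured covariance. The pediatric share was 0.305 and the fitted age effect 0.568.

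| Week 24 | AGE in CLASS, two proportions | AGE numeric, first coefficient only |
|---|---|---|
| Placebo mean (SE) | 2.724 (0.630) | 2.502 (0.688) |
| Fosmetpantotenate mean (SE) | −0.370 (0.630) | −0.591 (0.695) |
| Difference (SE) | −3.093744 (0.891934) | −3.093744 (0.891934) |

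Both arms moved by −0.222 = (2 × 0.305 − 1) × 0.568. Their intervals widened by 9–10%, inside the 30% band above. Numeric AGE with the single adult proportion reproduced the first column exactly.

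**The case against.** The strongest reply is that nothing inferential changes. The primary contrast and the gatekept test of UPDRS Part III both rest on the treatment difference. The intended model is clear from the text and from the GLM code. The ESTIMATE statements are introduced as examples, contain unfilled placeholders and are printed after the RUN statement, so a programmer must complete them and would probably notice. If the software rejects the surplus coefficient, no wrong number can be published. Per-arm information is also available from the descriptive summaries and the ANCOVA sensitivity analysis.

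Much of this stands. It confines the point to per-arm output. The SAP text itself promises confidence intervals for the difference; the per-arm intervals rest on the protocol sentence and the option in the code. The carry-over to exploratory scales is looser than to UPDRS Part III, because several of those sections ask only for a similar model.

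It does not remove the error. The example wording generalizes the week, and the SAP says these statements will be used. With no LSMEANS statement in the MIXED code, they are the stated route to the adjusted arm means of the primary model. The descriptive tables and the ANCOVA are different analyses. A repair made silently during programming would be an undocumented departure from the prespecified code.

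**Conclusion.** The concern holds. As written, the code yields per-arm adjusted means evaluated at the wrong age share, or no per-arm means. The primary treatment difference, its interval and its p-value are sound, so this is a reporting error to correct and not a threat to the trial's conclusion.

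The mismatch itself is certain. Its effect on the numbers is conditional: it assumes that the first coefficient is used and the second ignored, and its size depends on a pediatric share and an age effect that the documents do not give. The point estimates would be right only with a 50:50 age split or no age effect, and the intervals only with a 50:50 split. The plan guarantees neither. The width ratios also assume complete data and equal age shares in the two arms.

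**What to change.** In SAP 4.10.1, add AGE to the CLASS statement of the PROC MIXED code and keep the two proportions. Alternatively, leave AGE numeric and give it one coefficient, the proportion in age group 1. The two give identical results. Apply the same correction wherever the model is reused. This changes one line of code before database lock, with no cost in data, sample size or timeline.

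Two separate tidying points could go into the same SAP revision:
- The sentence beginning "To estimate the treatment effect (i.e., the difference between fosmetpantotenate and placebo) at Week i" lists Weeks 3, 6, 8, 12 and 24. The visits are Weeks 3, 6, 12, 18 and 24.
- The SAP text calls patient a random effect, while the code models within-patient covariance through a REPEATED statement with an unstructured matrix. The SAP wording can be aligned with the code at once. Protocol 12.9.1 and the synopsis carry similar wording; changing them would need an amendment under protocol 13.3, so that part is not free and can wait for the next amendment.

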4.2 Determination of Sample Size

It is estimated that a total of 74 patients (37 in each treatment group) will provide approximately 80% power to detect a 3-point difference between groups in the average change from baseline score for the PKAN-ADL, based on Student's t-test with alpha=0.05 (two-sided); this calculation assumes a standard deviation of 4.5 points for the change from baseline scores. Allowing for 10% attrition, a total of 82 patients will be randomized to achieve the target sample size of at least 74 patients completing the double-blind period of the study.

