Figures will be presented which show the PKAN-ADL total score for each visit during the double-blind period, as well as change from baseline score, by treatment group. This will be run using the Double-Blind FAS and repeated using the PPS.

In addition, a by-patient listing will be provided, which presents PKAN-ADL scores (total and for each item) across all assessments in the double-blind and open-label periods for patients in the Double-Blind FAS.

The change from baseline in PKAN-ADL total scores will be used to test the following hypotheses:

Null hypothesis:

There is no difference between the fosmetpantotenate and placebo groups, as measured by the change in PKAN-ADL total score from baseline to the end of the 24-week double-blind treatment period, with adjustment for age group and baseline PKAN-ADL total score.

Alternate hypothesis:

There is a difference between the fosmetpantotenate and placebo groups, as measured by the change in PKAN-ADL total score from baseline to the end of the 24 week double-blind treatment period, with adjustment for age group and baseline PKAN-ADL total score.

That is:

H_0 : Change from baseline PKAN-ADL Total Score at Week 24 (fosmetpantotenate) = Change from baseline PKAN-ADL Total Score at Week 24 (Placebo) *estimated via repeated measure analysis, with adjustment for age group and baseline score*

H_1 : Change from baseline PKAN-ADL Total Score at Week 24 (fosmetpantotenate) \neq Change from baseline PKAN-ADL Total Score at Week 24 (Placebo) *estimated via repeated measure analysis, with adjustment for age group and baseline score*

The primary efficacy analysis will be based on the FAS population in the double-blind period of the study. For each patient, the change from baseline in PKAN-ADL total scores at Weeks 3, 6, 12, 18, and 24 of the double-blind period will be used for analysis. The treatment effect will be evaluated on the basis of a mixed model for repeated measures (MMRM) analysis to assess data from all visits simultaneously. The model will include fixed effects for treatment, age group (pediatric, adult), visit and treatment by-visit interaction, with visit as the repeating factor and patient as a random effect, and baseline PKAN-ADL total score as a covariate. The PKAN-ADL total score obtained prior to the first dose of investigational product will serve as each patient's baseline value.

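### The primary MMRM fits one baseline PKAN-ADL slope for all visits, which can cost precision at Week 24; a baseline-by-visit term is a cheap improvement (minor)

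*SAP*

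**What the plan says.** SAP section 4.10.1 describes the fixed effects as treatment, age group, "visit and treatment by-visit interaction, with visit as the repeating factor and patient as a random effect, and baseline PKAN-ADL total score as a covariate". Its code matches: "model C_score = BASE_score AGE TRT WEEK TRT*WEEK / solution", followed by "repeated WEEK / subject=PATIENT type=un". The response is change from baseline at five visits, Weeks 3, 6, 12, 18 and 24. The only interaction with visit is treatment by visit. The protocol (Synopsis, Statistical Methods, and section 12.9.1) lists the same fixed effects.

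One visit decides the trial: "The primary treatment comparison will be based on the test of contrast between treatment effects using the LSM estimate at Week 24".

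SAP section 4.10.1.1 adds ANCOVAs fitted separately at each week as sensitivity analyses, and these give Week 24 its own baseline slope. For sample size, SAP section 4.2 states that "a total of 74 patients (37 in each treatment group) will provide approximately 80% power to detect a 3-point difference between groups", using an unadjusted t-test with an SD of 4.5 for the change score.

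**The concern.** The model is flexible in its covariance (unstructured) and in its treatment effect (free at each visit), but it holds the relation between baseline and change fixed over 24 weeks. The Week 24 difference is therefore adjusted with a slope estimated from all five visits. If the Week 24 slope is different, the adjustment there is incomplete and the standard error is larger than it needs to be.

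A changing slope is plausible. Protocol section 6.4 stresses heterogeneity in rate of progression, and if that rate varies with severity, the slope would tend to grow with time. The documents do not show that it does.

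At stake is some precision in the only confirmatory comparison of a trial with 82 randomized patients. The primary result also gates the test of UPDRS Part III (SAP section 4.10.4).

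**Working it through.** **Inputs from the documents.** 37 per arm, 3-point difference, SD of Week 24 change 4.5, two-sided alpha 0.05 (SAP 4.2); five visits, unstructured covariance, Week 24 contrast (SAP 4.10.1).

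**Assumed, because the documents do not give them.** Baseline SD 9, baseline slopes at each visit, and SDs and correlations of change across visits. Complete data; age group left out.

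**Step 1: the plan's own figure.** Noncentrality = 3 / (4.5 × √(2/37)) = 2.87, which gives 80.8% power by the noncentral t. The stated 80% is reproduced, with no credit for baseline adjustment.

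**Step 2: the common slope.** Let b be the five visit-specific slopes and S the residual covariance. The single fitted slope is bc = w′b, with w = S⁻¹1 / (1′S⁻¹1). The Week 24 variance, relative to a model with visit-specific slopes, is

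ratio = 1 + (b24 − bc)² × SDbase² / σ24².

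**Step 3: main scenario.** The slope grows in proportion to time to −0.2 at Week 24, so the baseline-change correlation there is −0.2 × 9 / 4.5 = −0.4. Then σ24² = 20.25 − 3.24 = 17.01. With equal variances and exchangeable correlation, every visit has weight 0.20, so bc = −0.105 and the ratio is 1 + 0.095² × 81 / 17.01 = 1.04. Visit-specific slopes give 87.0% power. With correlation 0.7 (per 6 weeks for AR):

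| Residual SD across visits | Correlation | Weights, Weeks 3/6/12/18/24 | Ratio | Power, one slope | Loss (points) |
|---|---|---|---|---|---|
| Equal | Exchangeable | 0.20/0.20/0.20/0.20/0.20 | 1.04 | 85.6% | 1.4 |
| Equal | AR | 0.34/0.08/0.11/0.11/0.36 | 1.04 | 85.8% | 1.2 |
| Doubling by Week 24 | AR | 0.96/−0.10/0.03/0.01/0.10 | 1.12 | 83.2% | 3.8 |
| Doubling by Week 24 | Exchangeable | 0.94/0.40/0.02/−0.15/−0.21 | 1.23 | 79.5% | 7.5 |

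In the last row the fitted slope is +0.019, on the wrong side of zero, which is why power falls below the unadjusted 80.8%.

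**Step 4: other slope patterns.** Slopes and total SDs change linearly with week. Ranges cover AR 0.85 per 6 weeks, AR 0.7 per 6 weeks and exchangeable 0.7. Entries are points of power lost.

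| Slope, Week 3 to 24 | SD 2.5 to 4.5 | SD 3.5 to 4.5 | Equal SD |
|---|---|---|---|
| −0.20 throughout | 0 | 0 | 0 |
| −0.10 to −0.20 | 1.1–2.3 | 0.6–1.2 | 0.3 |
| −0.03 to −0.20 | 2.9–6.3 | 1.7–3.2 | 0.7–0.9 |
| −0.05 to −0.25 | 3.6–8.3 | 2.0–3.4 | 0.5–1.0 |

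**Step 5: baseline SD.** A total score of 0 to 48 with entry at 6 or more leaves a span of 42. A uniform spread over it has SD 42/√12 = 12.1, so 12 is a high value. Repeating Step 3 with baseline SD 12 and the same slope (correlation −0.53) takes power from 91.7% to 89.3–89.7% with equal variances, 85.1% with growing variance and AR, and 78.6% with growing variance and exchangeable correlation. With a baseline-change correlation of 0.2 or less, the ratio is at most about 1.05.

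**Step 6: simulation of the Step 3 settings.** With 6,000 trials per setting, 37 per arm, the variance ratios were 1.04 to 1.24 with growing slopes and 0.99 to 1.00 with a constant slope. Type I error of the one-slope model was 0.044 to 0.052. The extra term cost no visible precision when the slope was constant.

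**The case against.** The strongest reply is that the size of the loss rests on inputs the plan does not contain. A reader might infer that this model always ties Week 24 to a slope set mostly by the early visits. The documents do not support that. The weights depend on a covariance that is not given, and with equal visit variances Week 24 itself carries 20% to 36% of the weight in the Step 3 settings. Early dominance needs the variance of change to grow over time, which is plausible but assumed.

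The larger losses also need a baseline-change correlation that rises sharply. If that correlation is held constant at 0.2 to 0.4 while the SD grows from 2.5 to 4.5, the slope still nearly doubles, but the loss is only 0.3 to 1.1 points with AR correlation of 0.85 per 6 weeks, and 0.4 to 1.6 points with exchangeable correlation of 0.7.

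The by-visit ANCOVA would also make any material difference at Week 24 visible.

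All of this stands, and it is why the point is minor. It does not remove the point: the ANCOVA is a sensitivity analysis and cannot change the primary p-value, and the restriction gains nothing visible in return.

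**Conclusion.** The concern holds as a conditional loss of efficiency. At an assumed baseline SD of 9, the loss is:

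- none with a constant slope;
- about 1 point of power (0.3 to 1.4) with equal visit variances;
- about 1 to 2 points with mild slope growth;
- about 4 points or more only when growing variance and a steeply rising slope occur together, up to about 7 to 9.

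A baseline SD of 12 would raise the upper end (13.1 points in the most extreme case in Step 5).

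Two stronger readings are not supported. First, a reader might infer that the trial misses its stated 80% power. That figure comes from an unadjusted t-test, and in most scenarios the one-slope model still exceeds 80.8%. It falls below only in the more extreme settings with growing variance and exchangeable correlation. Second, a reader might infer that the primary test is biased or has inflated type I error. Simulated type I error was close to nominal with complete data. Bias from dropout related to earlier scores was not examined, so nothing is claimed about it.

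Severity: minor.

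**What to change.** Before unblinding:

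- Add BASE_score*WEEK to the MODEL statement in SAP section 4.10.1.
- In the group-mean ESTIMATE statements, add the matching coefficient at mean baseline for the week being estimated. The treatment-difference ESTIMATE needs no baseline coefficient.
- Use the same term in the UPDRS Part III MMRM (SAP 4.10.2), the exploratory MMRMs (SAP 4.10.3) and the analytic model of the tipping-point analysis (SAP 4.10.1.2).
- Align the model wording in SAP section 4.10.1 and in the protocol (Synopsis and section 12.9.1).

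The cost is four more fixed-effect parameters in the five-visit models and small edits to the SAP and protocol text. It needs no new data, and no loss of Week 24 precision was visible even when the slope was constant.
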